1. GENERAL INFORMATION

1.1 Protocol Title

Implementation of the *Choose to Move* program in Sydney Australia

1.2 Protocol identifying number

Version 3.0, 02/09/2024

1.3 Sponsor and funding

The University of Sydney will be the sponsor of this study.

The NHMRC-CIHR Healthy Cities Implementation Science Team Grant Scheme grant (APP 2018862) will be funding the study. This is under the project title “Choose to Move Sydney”.

1.5 Collaborations

Our research team are collaborating in partnership with the Active Aging Research Team from the University of British Columbia who developed, implemented, and scaled up the *Choose to Move* program in Canada.

Our research team will engage with Sydney-based organisation SHARE (not-for-profit organisation), who offer low-cost exercise programs to people aged 50+, as our delivery partner for this research. We will adapt the *Choose to Move* program to achieve the best fit for the local context. We will identify specific implementation strategies (e.g. training, recruitment) that align with the priorities and capacity of the delivery partner SHARE.

1.6 Trial Registration

The study will be registered with the Australian New Zealand Clinical Trials Registry (ANZCTR) <http://www.anzctr.org.au> prior to commencement.

2. SYNOPSIS

TITLE	Implementation of the Choose to Move program in Sydney Australia
OBJECTIVES	This study has the following core objectives: 
 1. Describe adaptation of the Choose to Move program and implementation strategies to achieve “best fit” for older adults in Sydney. 2. Evaluate implementation of CTM programs, including use of implementation strategies. 3. Evaluate the acceptability and adherence of the Choose to Move program for older adults in Sydney. 4. Evaluate program effectiveness- measure if the Choose to Move program benefits health outcomes (e.g., physical activity, mobility, social isolation) in older adults in Sydney.
PRIMARY HYPOTHESIS	We hypothesise: 
 1. The Choose to Move program and implementation strategies will require minor adaptations to suit the needs of people aged 50 and over in Sydney. 2. The Choose to Move program will be implemented with fidelity. 3. The Choose to Move program will be acceptable and well attended by people aged 50 and over in Sydney. 4. The Choose to Move program will provide benefits to health outcomes to people aged 50 and over in Sydney.
DESIGN	This is an uncontrolled, single group implementation study that is focused on implementing the Choose to Move program in Sydney, Australia. This will be through a process of: 
 1. Adaptation: Co-design adaptation of the program and implementation strategies for adults in Sydney 2. Program implementation and delivery: build organisation capacity and support delivery partners on implementation, deliver 3-month intervention. 3. Evaluation: Describe and assess implementation strategies used to achieve ‘best fit’ and to measure Choose to Move program benefits for various health outcomes.
BLINDING / MASKING	Open (masking not used)


OUTCOMES
	
Primary effectiveness outcome: Physical activity (PA) will be assessed using the single item measure of self-reported number of days engaging in at least 30 minutes of moderate physical activity per week.
 
Secondary effectiveness outcomes: Self-reported single item questions about days per week doing muscle strengthening activities and balance training, ability to walk 400m and 1 flight of stairs, health limitations affecting activities, sedentary behaviour, quality of life, social isolation, loneliness, perception of balance, fear of falling, number of falls in past 12 months, adverse events at follow up and Short Physical Performance Battery.
 
Implementation outcomes: Reach, adoption, fidelity, dose, sustainability.
 
Implementation determinants: Acceptability, cost, feasibility, adaptability, compatibility, culture, complexity, self-efficacy
 
Qualitative outcomes: Participant acceptability, barriers, facilitators, and participant experience.
 
Cost outcomes: Study-specific logs will be used to record costs associated with design, adaptation and intervention delivery and could be used to create a decision analytic model to conduct a simulated cost-effectiveness analysis.

STUDY DURATION
	
We aim to recruit all participants between Oct 2024 and December 2026. Data analysis and report writing will be completed by December 2027.

INTERVENTION/S
	
Choose to Move is a 3-month program that provides motivation and support for adults aged 50 years and over to become more physically active and socially connected. Participants work with a trained activity coach in groups to set health goals and develop a personalised physical activity plan.
 
The program involves:
 
 • One-one consultation action planning (30min). • Group meetings (8x1 hour sessions over 3 months): Activity coaches will deliver education on various health topics, share community resources and facilitate group discussions. • Access to the Choose to Move website. • Access to the Choose to Move Facebook group. • Resources - group meeting PowerPoint presentations, handouts and fortnightly newsletters).

NUMBER OF PARTICIPANTS
	
16 programs with average of 10 participants per program will provide a total of 160 participants.


POPULATION
	
160 adults aged 50+ living in the community (Sydney, Australia) and who are not currently meeting physical activity guidelines and would like support to be more physically active.

SELECTION AND ENROLMENT
	
Inclusion Criteria
 
The study will involve consenting adults who:
 
 1. aged over 50. 2. consider themselves inactive (do less than 150 minutes of moderate physical activity per week).

	
 3. want to receive physical support to be more active. 4. able to commit to a 3-month program. 5. live in the community across Sydney. 
Exclusion Criteria
 
The study will exclude adults who:
 
 1. have insufficient English language skills to fully participate in the program. 2. have a medical condition that precludes participation in regular physical activity. 3. have a diagnosed cognitive impairment. 4. have a progressive neurological disease (e.g., Parkinson's disease). 5. are unable to leave the house independently and walk 10 metres unassisted.
--	--

3. RATIONALE / BACKGROUND

The World Health Organization (WHO) estimates that between 2015 and 2050, the proportion of the world's population over 60 years of age will nearly double from 12% to 22%. The pace of population ageing is increasing, and "all countries face major challenges to ensure that their health and social systems are ready to make the most of this demographic shift"¹. Australia's population, along with the global population, is ageing. In 2020 there were more than 4 million people in Australia who were aged 65 and over. The proportion of people aged 65 and older is expected to grow by 31% by 2030 and by 55% by 2040².

The physical activity guidelines for people aged 65+ recommend that they engage in at least 30 minutes of moderate intensity physical activity on most, preferably all, days. Despite the many benefits of physical activity, only 41.8% of older Australians are meeting these guidelines³. Physical activity participation has enormous untapped potential as a cost-effective approach to enhancing health in people of most ages, health conditions and physical abilities⁴. A Lancet editorial⁴ calls for physical activity to be taken more seriously as a population health intervention, given the strong evidence of physical and mental health benefits yet poor participation rates. As well as prevention and management of chronic conditions, physical activity is now known to have survival benefits⁵.

Choose to Move (CTM) is a community-based program, co-designed with older adults, that increases physical activity and mobility and reduces social isolation⁶. *Choose to Move* integrates behaviour change principles into two components:

1. One-to-one consultation action plan meeting
2. Motivational activity coach-led group sessions

The *Choose to Move* program was successfully developed and implemented in Canada by the Active Aging Research Team at the University of British Columbia, with funding from the Government of British Columbia. *Choose to Move* was rigorously developed with implementation science principles. It is scalable, co-designed, adaptable, tailored for communities, and based on authentic partnerships.

Social connectedness and loneliness are important aspects of the *Choose to Move* program. Social connectedness is defined as 'feelings of interpersonal connection and meaningful, close, and constructive relationships with others (individuals, groups, and society)⁶. A socially connected person feels that they; care about others and are cared about by others and belong to a group or community. Caring and respect in social relationships prompts a sense of well-being together they act as a buffer against health problems and catalyse myriad health benefits⁷. Loneliness is a perceived lack in quality or quantity of one's relationships⁸ and is closely linked with accelerated loss of physical functioning and health with age, and an increased likelihood that an older person discontinues PA over time^{9,10}.

Researchers are now advocating for interventions that aim to enhance social connectedness and reduce loneliness in older people¹¹.

Choose to Move program has not been implemented in Australia, so this research will generate new knowledge of how this intervention can be scaled up to promote health in adults aged 50 and over. This research will bring enormous benefit to Australia in terms of new knowledge, researcher capacity building and international collaboration for knowledge exchange. We will target people in Sydney, who are currently insufficiently active and who would like support to be more active. The World Health Organisation 2018 Global Action Plan on Physical Activity set a global target of 15% improvement in physical activity by 2030. Our research will help Australia reach this target and align with the World Health Organisation's call for research investment in strategies that support people to maintain physical activity capacity in their older age.

4. AIMS / OBJECTIVES / HYPOTHESES

This research study main objectives will be to adapt and implement the *Choose to Move* program to the Australian context. The study core objectives are as follows:

This study has the following core objectives:

1. Describe adaptation of the *Choose to Move* program and implementation strategies to achieve "best fit" for older adults in Sydney.
2. Evaluate implementation of CTM programs, including use of implementation strategies.
3. Evaluate the acceptability and adherence of the *Choose to Move* program for older adults in Sydney.
4. Evaluate program effectiveness- measure if the *Choose to Move* program benefits health outcomes (e.g., physical activity, mobility, social isolation) in older adults in Sydney.

We hypothesise:

1. The *Choose to Move* program and implementation strategies will require minor adaptations to suit the needs of people aged 50 and over in Sydney.
2. The *Choose to Move* program will be implemented with fidelity.
3. The *Choose to Move* program will be acceptable and well attended by people aged 50 and over in Sydney.
4. The *Choose to Move* program will provide benefits to health outcomes to people aged 50 and over in Sydney.

5. PARTICIPATING SITES

The study will be conducted across metropolitan areas of Sydney where our delivery partner organisation SHARE is based. In addition, occasional online classes (via zoom) may be made available if there is a demand for those who cannot access a community organisation site.

Current delivery partner organisations include:

- SHARE (non-for-profit organisation) who has multiple sites across metropolitan areas of Sydney.

6. RESEARCH PLAN / STUDY DESIGN

6.1 Type of study

This is an uncontrolled, single group implementation study that is focused on implementing the *Choose to Move* program across Sydney, Australia. This will be through a process of:

1. Adaptation: Co-design implementation strategies to adapt the program for adults in Sydney.
2. Intervention: Deliver 3-month intervention, build organisation capacity and support delivery partners on implementation
3. Evaluation: Measure the acceptability and adherence of the CTM program
4. Evaluation: Describe and assess implementation strategies used to achieve 'best fit' and to measure CTM program benefits for various health outcomes.

6.2 Population / Sample size including power calculation.

16 programs with an average of 10 participants per program will provide a total of 160 participants to detect a difference in the proportion of participants who increase their physical activity level from baseline to 3-months (approximately 1 day/week), allowing for 20% dropout.

Sample Size: To attain >80% power to detect an increase in PA of approximately 1 day/wk as per CTM Phase 3 (PA by the single-item measure; T1 = 2.5 d/wk.; T2 = 3.4 d/wk.; SD difference = 2.2) with alpha of 0.05 across two comparisons (T2 vs.T1), an intraclass correlation for PA of 0.05 (to account for the clustered design of participants within programs) and estimated 20% drop out.

6.3 Study duration

The study is expected to take four years. We aim to recruit all 160 participants within the first 2.5 years of the study. This will allow time to complete the follow-up and data analysis. Participant follow-up, data analysis and report writing will be completed within the 4-year grant timeframe, as outlined in Table 1.

Table 1: Study timeline (n= 160) and recruitment plan

Task	Year 1	Year 2	Year 3	Year 4
Ethical approval, recruit staff, finalise intervention sites and procedures	✓			
Participants recruited in total	20	70	70	00
Participants completed 3- and 9-month follow-up in total	20	70	70	70
Data entry/ checking	✓	✓	✓	✓
Data analysis and manuscript draft completed.				✓

6.4 Statistical analyses

Analyses will be guided by a rigorous statistical analysis plan developed a priori as we have done previously. Continuous primary and secondary outcomes will be analysed using linear regression. Dichotomous secondary outcomes will be analysed with chi-squared tests. Analyses will be conducted using Stata 14 software.

6.5 Recruitment and selection of participants, delivery partner organisations and activity coaches

Participants

Advertising for participants will be undertaken through the general community via social media advertising and through our partner community organisation. We will advertise using our recruitment flyers in newsletters, websites, and social media [Facebook, LinkedIn, and X (formerly known as Twitter)]. The delivery partner organisation will use our recruitment flyer on their social media accounts, websites and in their newsletters. The advertising across social media will occur on an as needed basis. Paid advertisements will run for 5-7 days at a time. The paid advertisements will target different areas of Sydney (e.g., advertisement may target a specific area where a partner organisation resides and will run the program from) thereby not spamming the same people with every advertisement.

The recruitment flyer will have a link or QR code that will take potential participants to a screening survey that will be hosted on REDCap on the University of Sydney server. Here participants will have access to the most up to date ethics approved Participant Information Statement. People who wish to participate or find out more information will provide their contact details and consent for a member of the research team to telephone them to discuss the program in more detail. Screening for eligibility will only be conducted by The University of Sydney research team. Prior to assessing for eligibility, the research team will explain that the participant may be required to disclose some personal information and participants will be asked to provide verbal consent to do so. People who do not meet the eligibility criteria, or choose not to participate, will have any identifiable information destroyed.

If participants are eligible, they will be invited to attend an information session 1-2 weeks before the program starts to provide more detail and help decide if *Choose to Move* is right for them. Consent to

participate in the *Choose to Move* program will be obtained by researchers at The University of Sydney not the partner organisations (SHARE). Consent will be obtained online or paper based written form.

Delivery partner organisation

Our research team will engage with Sydney-based organisation SHARE (not-for-profit organisation), who offer low-cost exercise programs to people aged 50+, as our delivery partner for this research. No recruitment will be necessary.

Activity Coaches

Activity coaches that will be used to deliver the *Choose to Move* program are already part of the University of Sydney research team or group fitness leaders' employees of SHARE. No recruitment will be necessary. No formal qualification is needed to be an activity coach on the *Choose to Move* study just experience with working with adults aged 50 and over.

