6.5.4 Schedule of events

The timing of the *Choose to Move* intervention components over the 12-week period is outlined in Table 2. The timing for measures collected for relevant stakeholders are outlined in Table 3.

Table 2: *Choose to Move* component delivery timeline.

Program Week		1	2	3	4	5	6	7	8	9	10	11	12
Information Session	●												
Motivational Group Meeting		●		●	●	●	●		●		●		●
One-on-One Consultation			●										

[figure not shown]
Note: the weeks may be slightly adjusted based on room availability at the delivery organisations venue and other unforeseen events such as public holidays.

Table 3: Overview of measures collected for each participant group and various time points.

Participant group	Measures	Planning (T0)	Baseline of Program (T1)	3 months (on completion of program) (T2)	9 months (6 months post program) (T3)
Participants	Demographic and Get Active Forms		Y		
	Outcome measures survey		Y	Y	Y
	Impressions of the choose to move program survey (end of program feedback)			Y	
	Interviews (subset) end of program			Y	
Activity Coach	Training Survey	Y			
	Feedback Survey			Y	
	Interview (subset) end of program			Y	
Organisations representatives (Director/manager) (SHARE)	Feedback Survey end of program			Y*	
	Interview (Directors/manager) end of program			Y*	

*Follow up survey and interview by organisation representative will only be completed at the end of the last program delivery.

Figure 1. Flow of participants

Choose to Move and implementation strategies for Sydney

The research project team will engage with participants and partner organisation SHARE in an adaption process to adapt the *Choose to Move* program to achieve the best fit and identify specific implementation strategies (e.g. training, recruitment) that align with the priorities and capacity of the delivery partner SHARE that will implement the program.

What support do organisations receive?

The team at the University of Sydney will work with partner organisation SHARE to understand how *Choose to Move* might fit and complement their existing programs and activities (Table 4). SHARE will receive funding to cover delivery costs for staff.

Table 4: The support provided to organisations (implementation strategies).

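### The sample size allows for clustering within programs, but the linear regression named for the primary outcome has no term for program

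*Protocol*

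**What the plan says.** Section 6.2 plans the study in groups: "16 programs with an average of 10 participants per program will provide a total of 160 participants". The power statement is for a change between two visits in the same people, with "T1 = 2.5 d/wk.; T2 = 3.4 d/wk.; SD difference = 2.2", and it includes "an intraclass correlation for PA of 0.05 (to account for the clustered design of participants within programs", plus an allowance for 20% dropout.

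Section 6.4 gives the analysis in three short statements. The first defers to a separate document: "Analyses will be guided by a rigorous statistical analysis plan developed a priori as we have done previously". The second is the one that governs the primary test: "Continuous primary and secondary outcomes will be analysed using linear regression". The third deals with yes/no endpoints: "Dichotomous secondary outcomes will be analysed with chi-squared tests". Program, participant, visit, change score and baseline adjustment are not mentioned.

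Table 3 in section 6.5.4 has each participant complete the outcome survey at baseline (T1), 3 months (T2) and 9 months (T3). There is no control group, so the effect is a change over time within people.

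**The concern.** The two sections describe different data. Section 6.2 treats people in the same program as correlated and allows for that in the sample size. Section 6.4 names a method whose usual standard error assumes independent observations. Members of one program share a coach, a venue and group sessions, so their changes may well move together. If so, an analysis that leaves program out claims more precision than the data hold.

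This is the primary effectiveness test, and the same sentence governs the continuous secondary outcomes. At stake are the reported interval and p-value, above all for effects smaller than the one planned for.

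**Working it through.** **Inputs**

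- Section 6.2: 16 programs, average 10 people, 160 recruited; T1 2.5 and T2 3.4 days/week, so a change of 0.9; SD of the difference 2.2; ICC 0.05; dropout 20%.
- Derived: 160 × 0.8 = 128 completers, and 128 / 16 = 8 per program.
- Assumed: a two-sided test (not stated), equal program sizes, and an ICC of 0.05 for the change. The protocol states the ICC for physical activity only, so a range follows in step 4.

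**1. The plan's own figure.** For a paired change at 80% power and alpha 0.05, n = (SD × (1.960 + 0.842) / change)² = (2.2 × 2.802 / 0.9)² = 46.9. With clustering and dropout:

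- 8 per program: 46.9 × 1.35 / 0.8 = 79.1, so 80 recruits.
- 10 per program: 46.9 × 1.45 / 0.8 = 85.0, so 86 recruits.
- At alpha 0.025, one reading of "alpha of 0.05 across two comparisons (T2 vs.T1", the need is 96 to 103.

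So 160 recruits give more than 80% power, as stated. Treating T1 and T2 as independent samples gives 2 × 46.9, or 94 after rounding up, and 94 × 1.35 / 0.8 = 158.6, so 159. That is close to 160, but it does not show how 160 was reached.

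**2. Design effect.** DE = 1 + (m − 1) × ICC.

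- m = 8: 1 + 7 × 0.05 = 1.35; square root 1.162.
- m = 10: 1 + 9 × 0.05 = 1.45; square root 1.204.

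**3. Regression of change with program ignored (128 completers, m = 8)**

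- Standard error as computed: 2.2 / √128 = 0.194; half-width 1.96 × 0.194 = 0.38 days/week.
- Standard error needed: 0.194 × 1.162 = 0.226; half-width 0.44 (0.48 with a t-value on 15 degrees of freedom).
- Interval too narrow by 1 − 1/1.162 = 14% (m = 10: 1 − 1/1.204 = 17%).
- Type I error = 2 × (1 − Φ(1.96 / √DE)) = 9.2% at m = 8 and 10.4% at m = 10. Coverage is therefore 90.8% and 89.6%.
- At a nominal 2.5% level the error is 5.4% and 6.3%.

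A simulation of 20,000 studies with 16 programs of 8 gave 9.4% for the test that ignores program. A t-test on the 16 program means gave 5.1%.

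**4. Range over the ICC of change (assumed values; m = 8 to 10)**

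| ICC of change | Design effect | Type I error |
|---|---|---|
| 0 | 1.00 | 5% |
| 0.01 | 1.07-1.09 | 5.8-6.1% |
| 0.02 | 1.14-1.18 | 6.6-7.1% |
| 0.05 | 1.35-1.45 | 9.2-10.4% |
| 0.10 | 1.70-1.90 | 13-16% |

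**5. If visits were stacked with no participant term.** The standard error is then too large by 1/√(1 − r), where r is the correlation between a person's two visits. The protocol gives no r. At assumed values of 0.2, 0.5 and 0.7 the factor is 1.12, 1.41 and 1.83. Combined with an ignored design effect of 1.35, the net type I error is 5.9%, 1.7% and 0.2%.

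**6. Power with clustering respected.** With 128 completers and a change of 0.9, power is 95-98% at alpha 0.05 and 90-96% at 0.025. The ranges cover m = 8 and 10, with normal and 15-degree-of-freedom reference values.

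**The case against.** The strongest reply is that section 6.4 does not exclude clustering. It defers to a statistical analysis plan that is not at hand. How standard errors are computed is a detail often left to such a plan, and linear regression with program-clustered errors is still linear regression. The authors plainly knew of the clustering. This stands in part: a reader might infer that the primary interval and p-value will be wrong, and the documents do not support that. They would be wrong if the analysis were run as written with no allowance for program. But section 6.4 is not silent. It names a method, and that method as stated omits the correlation that section 6.2 allows for.

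A second tempting inference is that the analysis also ignores the repeated measures. The unpaired chi-squared test for dichotomous outcomes, and the near match of 159 to 160 when visits are treated as independent, make this plausible. They do not establish it for the primary outcome. Section 6.2 works with the SD of a difference, and a regression of change has one row per person. The fault arises only if visits are stacked without a participant term. It would then widen the interval, the opposite direction to ignored clustering.

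Third, an ICC for activity levels is not an ICC for change. A stable program effect on levels cancels when each person's baseline is subtracted, and the change-score test would then keep its 5%. This stands, and is why the 9-10% is conditional and comes with a range.

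Finally, at the planned change of 0.9 days/week the conclusion would very probably be the same either way. That is fair and bears on severity.

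**Conclusion.** The mismatch is real: the design allows for program clustering, and the stated analysis does not carry it through. The 14-17% shortfall in interval width, 90-91% coverage and 9-10% type I error rest on three conditions: change is regressed with program left out, the ICC of change is 0.05, and programs have 8 to 10 people in the analysis. The error would be smaller with a lower ICC of change and larger with a higher one. No second fault from repeated measures is shown. The sample size stands. This should be fixed, because the sentence governs the primary test, but it does not put the study's conclusion at risk if the effect is as large as planned.

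**What to change.** State in section 6.4, and carry into the analysis plan, that continuous outcomes will be analysed by a method that respects program clustering and within-person pairing. Either of two would match section 6.2:

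- regression of change with program-level cluster-robust standard errors and a small-sample correction for 16 clusters; or
- a linear mixed model with time as a categorical fixed effect, a random intercept for participant, and random program and program-by-time effects, with small-sample degrees of freedom. The program-by-time term is needed because a program intercept alone cancels out of the change.

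A t-test on the 16 program mean changes (15 degrees of freedom) is a simple check on either.

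The cost is one sentence and no new data. The interval becomes slightly wider: at an ICC of change of 0.05 and 8 completers per program, ±0.44 days/week (±0.48 on 15 degrees of freedom) instead of ±0.38. Power at the planned 0.9-day change stays above 80%, so the number of programs and participants need not change.
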